## **1.2 Study rationale**

Human radiolabelled mass balance or absorption, distribution, metabolism and excretion (ADME) studies are required by regulatory agencies for the registration of new drug, and therefore, are an integral part of the drugs development programs.

This study along with data from the mass balance studies in toxicology species, provides essential information on the exposure of the parent compound and the metabolites of CHF6001.

It will be an open-label study in 8 healthy male participants aimed to assess the absolute bioavailability, the mass balance and routes of elimination of CHF6001 in humans, using [C]-radiolabelled drug substance administered as an intravenous (IV) infusion concomitantly to an inhaled non-radiolabelled dose.

The study involves a small amount of radioactivity; therefore, only adult males are included in the trial. It will be conducted as an open-label trial as the study measures are objective outcomes (eg, total radioactivity in select biological matrices). Conducting the study in healthy subjects will allow the evaluation of CHF6001 metabolism in the absence of concomitant medications. The dose, subject population, study duration, and sample collection timing are considered adequate to achieve the study objectives.

## **1.3 Risk/benefit assessment**

A single inhaled dose of CHF6001 3200 $\mu$ g DPI will be administered to healthy subjects in an open-label fashion. This dose (and higher inhaled doses up to 4800 $\mu$ g) had been assessed after repeated dosing (14 days) in healthy subjects and had proved to be safe and well tolerated [8].

A microdose was selected because CHF6001 has not previously been administered by IV infusion to humans, although testing has been conducted in pre-clinical studies [13] and in order to evaluate the mass balance and absolute inhaled bioavailability in the same setting, thus reducing the overall exposure of healthy volunteers to CHF6001. The radioactive dose administered in this trial is an acceptable dose for [C]-labeled human drug metabolism studies of this type. It is expected that this dose will provide a sufficient radioactive signal for total radioactivity counting and quantitative radioprofiling of [C]-CHF6001 in plasma and excreta with minimal radiation risk to subjects.

The volunteers will be followed at the clinical site and closely monitored throughout the study period.

This trial is a mass balance study, so no benefits are expected for the healthy volunteers. Considering the safety profile of the IMP, the minimal radiation risk to subjects, the measures in place to assure the patients' safety and the expected scientific value, the overall risk/benefit assessment can be considered acceptable for the proposed trial.

This trial will be conducted in compliance with the Declaration of Helsinki (1964 and amendments) current ICH E6 Good Clinical Practices and all other applicable laws and regulations.

Clinical Study Code: CLI-06001AA1-02	Version No.: 1.0
EUDRACT No.: 2020-004201-31	Date: 19 October 2020

## 2. STUDY OBJECTIVES

- To determine the absolute bioavailability of CHF6001 following single inhaled dose co-administered with an IV microtracer dose
- To characterize the mass balance and routes of elimination of CHF6001 after an IV microtracer dose
- To characterize the relevant metabolites in plasma, urine and feces
- To assess the safety and tolerability of the study treatment

## 3. STUDY DESIGN

This clinical trial is a single centre Phase I study, with a single dose, non-randomized, open-label, uncontrolled design.

### Screening

At screening visit (31 to 3 days before first study treatment administration), subjects will be selected to enter in the study according to the eligibility criteria. The signed informed consent form will be obtained prior to any study related procedures.

### Treatment Period

During the treatment period, subjects will remain at the clinical site (all subjects will be treated at [REDACTED] site) from Day -1 (the day before the study drug administration) until the morning of Day 11. Each subject will fast from 10 hours pre-dose until 2 hours post-dose (between 2 hours post dose and discharge, standard meals will be provided at standard times as per site practice). They will be discharged after the 240h post-dose (i.v.) assessments are completed.

### Follow-up

A follow-up phone call (or visit, if necessary) will be performed between 7 to 10 days after discharge or premature discontinuation to check and record concomitant medications and the status of any unresolved adverse events or occurrence of any new adverse events.

### End of the trial

The end of the trial is defined at execution of the Follow-up call (or visit) of the last subject of the trial.

## 4. SUBJECT SELECTION CRITERIA

### 4.1 Subject Recruitment

A total of 8 subjects will be included in the study.

Subjects will be screened by selection from the subjects' database of the clinical centre or via advertisement. Study specific advertisement will be submitted to the Ethics Committee for approval, before using it in the study.

Clinical Study Code: CLI-06001AA1-02	Version No.: 1.0
EUDRACT No.: 2020-004201-31	Date: 19 October 2020

## **4.2 Inclusion Criteria**

Subjects must meet all of the following inclusion criteria to be eligible for enrolment into the study:

1. Subject's written informed consent obtained prior to any study-related procedure;
2. Able to understand the study procedures, the risks involved and ability to be trained to use correctly the inhalers and to generate sufficient PIF (at least 40 L/min) using the In-Check device set as per NEXThaler® inhaler resistance and Placebo inhaler;
3. Male subjects aged 30 to 55 years inclusive;
4. Body mass index (BMI) within the range of 18 to 35 kg/m^2 inclusive;
5. Non- or ex-smoker who smoked < 5 pack years (pack-years = the number of cigarette packs (20 cigarettes) or equivalent per day times the number of years) and who stopped smoking > 1 year prior to screening;
6. Good physical and mental status, determined on the basis of the medical history and a general clinical examination, at screening and before treatment;
7. Vital signs at screening within limits defined as: Diastolic Blood Pressure 40-90 mmHg and Systolic Blood Pressure 90-140 mmHg, (three) measures performed in supine position after at least 5 minutes of resting. The average from triplicate measurements must be within the defined range;  
*Note: In case the values are outside the defined ranges, the assessment can be repeated once before treatment.*
8. 12-lead digitised Electrocardiogram (12-lead ECG) in triplicate considered as normal (40 ≤ Heart rate ≤ 110 bpm, 120 ms ≤ PR ≤ 210 ms, QRS ≤ 120 ms, QTcF ≤ 450 ms) at screening visit. The average from triplicate measurements must be within the defined range;  
*Note: In case the values are outside the defined ranges, the assessment can be repeated once before treatment.*
9. Lung function measurements within normal limits at screening: FEV1 >80% predicted and FEV1/FVC > 0.70;  
*Note: In case the values are outside the defined ranges, the assessment can be repeated once before treatment.*
10. Regular bowel movements (averaging one or more bowel movements per day) at screening;
11. Males fulfilling one of the following criteria:
  - a. Males with non-pregnant WOCBP partners: they and/or their partner of childbearing potential must be willing to use a highly effective birth control method in addition to the male condom from the signature of the informed consent and until 90 days after the follow-up visit or
  - b. Males with pregnant WOCBP partner: they must be willing to use male contraception (condom) from the signature of the informed consent and until 90 days after the follow-up visit or
  - c. Non-fertile male subjects (contraception is not required in this case) or
  - d. Males with partner not of childbearing potential (contraception is not required in this case).

Moreover, subjects must not donate sperm during the study and for 90 days after the follow-up visit. For the definition of WOCBP and of fertile men and the list of highly effective birth control methods, refer to [Appendix 2](#) (or section 4.1 of the CTFG guidance for more detailed information).

*Inclusion criteria 7, 8 and 9 could be checked again once before treatment.*

- *If the criteria are met after the re-check, the subject can continue the study.*

Clinical Study Code: CLI-06001AA1-02	Version No.: 1.0
EUDRACT No.: 2020-004201-31	Date: 19 October 2020

- *If the criteria are still not met, the subject will be discontinued and screen failed.*

*The inclusion criterion n. 6 will be re-checked at Day -1.*

- *If the criterion is met, subject can continue the study.*
- *If the criterion is not met, subject will be discontinued and screen failed.*

#### **4.3 Exclusion Criteria**

The presence of any of the following will exclude a subject from study enrolment:

1. Participation in another clinical trial with an investigational drug in the 3 months or 5 half-lives of that investigational drug (whichever is longer) preceding the administration of the study drug; a longer and more appropriate time could be considered by the principal investigator based on the elimination half-life and/or long-term toxicity of the previous investigational drug;
2. Clinically relevant and uncontrolled respiratory, cardiac, hepatic (including Gilbert syndrome), gastrointestinal, renal, endocrine, metabolic, neurologic, or psychiatric disorder that may interfere with successful completion of this protocol according to Investigator judgement;
3. Clinically relevant abnormal laboratory values at screening suggesting an unknown disease and requiring further clinical investigation or which may impact the safety of the subject or the evaluation of the study results according to Investigator judgement;  
*Note: In case of abnormal laboratory values, that could indicate a temporary condition, the test can be repeated once before treatment.*
4. Subjects with history of breathing problems (e.g. history of asthma including childhood asthma);
5. Positive to HIV1 or HIV2 serology at screening;
6. Positive results from the Hepatitis serology which indicates acute or chronic Hepatitis B or Hepatitis C at screening (i.e. positive HB surface antigen (HBsAg), HB core antibody (IgM anti-HBc), HC antibody);
7. Blood donation or blood loss (equal or more than 450 mL) less than 2 months prior screening or prior to treatment;
8. Positive urine test for cotinine at screening or before treatment;
9. Documented history of alcohol abuse within 12 months prior to screening or a positive alcohol breath test at screening or before treatment;
10. Documented history of drug abuse within 12 months prior to screening or a positive urine drug screen at screening or before treatment;
11. Intake of non-permitted concomitant medications in the predefined period prior to screening or before treatment) or the subject is expected to take non-permitted concomitant medications during the study (see “non-permitted concomitant medications” section);
12. Presence of any current infection, or previous infection that resolved less than 7 days prior to screening or before treatment;
13. Known intolerance and/or hypersensitivity to any of the excipients contained in the formulation used in the trial;
14. Unsuitable veins for repeated venipuncture;
15. Heavy caffeine drinker (> 5 caffeinated beverages e.g., coffee, tea, cola per day);
16. Abnormal haemoglobin level defines as <13mg/l for males and <11.3mg/l for female at screening;
17. Subjects using e-cigarettes within 6 months prior to screening;
18. Subjects been involved in a study involving a C-labeled drug within the 12 months prior to enrollment;

Clinical Study Code: CLI-06001AA1-02	Version No.: 1.0
EUDRACT No.: 2020-004201-31	Date: 19 October 2020

19. Subjects with exposure to significant diagnostic or therapeutic radiation (eg, serial X-ray, computed tomography scan, barium meal) or current employment in a job requiring radiation exposure monitoring within 12 months prior to Day-1;
20. Documented COVID-19 diagnosis within the last 8 weeks or which has not resolved within 14 days prior to screening and before treatment.

*The exclusion criterion 3, if met at the screening visit, can be checked again once before the treatment:*

- *If the criterion is not met after the re-check, the subject can continue the study.*
- *If the criterion is still met, the subject will be discontinued and screen failed.*

*The following exclusion criteria 7, 8, 9, 10, 11, 12 and 20 will be re-checked at Day -1 visit:*

- *If all the criteria are not met, the subject can continue the study.*
- *If at least one criterion is met, the subject will be discontinued and screen failed.*

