### 7.2.2 Blood collection for safety evaluation

The following blood samples will be collected at Screening and at discharge:

- **3.5 mL** of blood sample for serum **clinical chemistry testing** (creatinine, urea, aspartate aminotransferase (AST), alanine aminotransferase (ALT), Gamma-glutamyl transpeptidase ( $\gamma$ -GT), total bilirubin, alkaline phosphatase, sodium (Na), potassium (K)) and **fasting glucose**.
- **3.5 mL** of blood sample for serum **serology testing** (HIV1, HIV2, Hepatitis B and Hepatitis C) will be collected only at Screening.
- **4 mL** of blood sample for **haematology testing** (red blood cells count (RBC), white blood cells count (WBC) and differential (neutrophils, eosinophils, lymphocytes, monocytes) (% and values), total haemoglobin (Hb), haematocrit (Hct), platelets count (PLT)).

Below indications will be followed for safety evaluation in blood at screening:

- As for Exclusion criteria no. 3, in case clinically relevant abnormal laboratory values are observed, suggesting a temporary condition and requiring further clinical investigation, subject will be asked to return to clinic once before treatment, to perform again the testing measurement. If at that time no abnormalities are observed, subject can be included in the study, otherwise subject will be discharged and recorded as Screening Failure.

Blood collection and sample preparation will be performed according to procedures provided by the local laboratory which will be in charge to transmit the results and the laboratory normal ranges for entry in the eCRF.

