## APPENDIX 3 – BREAKDOWN OF BLOOD SAMPLES COLLECTION

### Detailed Blood Collection Volumes for PK sampling:

TOTAL VOLUME TO BE COLLECTED PER SUBJECT							
	Clinical chemistry & Fasting glucose	Hematology	Serology	Whole Blood AMS	PK	PK-AMS	Metabolite profiling
Screening	1	1	1				
Day -1							
Day 1				4	12	15	15
Day 2					1	1	1
Day 3					1	1	1
Day 4					1	1	1
Day 5					1	1	1
Day 6					1	1	1
Day 7					1	1	1
Day 8					1	1	1
Day 9					1	1	1
Day 10					1	1	1
Day 11	1	1			1	1	1
Follow up							
Total vol (mL) per sample	3.5	4	3.5	2	4	5	10
Tot vol (mL)	7	8	3.5	8	88	125	250
Total vol (mL) per subject	489.5

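### Exclusion criterion 16 prints the male haemoglobin limit as 13 mg/l (0.013 g/l), so as written it can exclude nobody; value and unit need confirming together

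*Protocol*

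**What the plan says.** Exclusion criterion 16 in Protocol Section 4.3 is "Abnormal haemoglobin level defines as <13mg/l for males and <11.3mg/l for female at screening". The exclusion list in the Protocol Outline prints it identically. Inclusion criterion 3 (Section 4.2) restricts the study to "Male subjects aged 30 to 55 years inclusive", so only the male figure could ever operate.

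Haemoglobin is part of the haematology panel in Section 7.2.2, where no unit or limit is given. On timing, that section says "The following blood samples will be collected at Screening and at discharge". Reference ranges are left to the "local laboratory which will be in charge to transmit the results and the laboratory normal ranges for entry in the eCRF". Screening falls "31 to 3 days before first study treatment administration" (Section 3), and discharge is on Day 11.

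The other laboratory criterion is exclusion 3. It has no numeric limits and turns on whether an abnormal value suggests an unknown disease needing investigation, or is one "which may impact the safety of the subject or the evaluation of the study results according to Investigator judgement". The SAP does not restate any haemoglobin limit.

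**The concern.** A numeric eligibility limit should separate subjects who may enter from those who may not. A limit of 13 mg/l is 13 thousandths of a gram per litre, far below any haemoglobin result a laboratory could report for a living adult. Applied literally, the criterion is always satisfied and does no work.

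What is lost is the protocol's only numeric haemoglobin cut-off. The sponsor wrote criterion 16 in addition to criterion 3, so something firmer than judgement was presumably wanted; as printed, only judgement remains. There is also a smaller effect on reporting. SAP Section 8.1.3 classifies protocol deviations, with breach of an exclusion criterion as one category. Read literally, enrolling a man with low haemoglobin would not breach criterion 16 and would not be recorded as such a deviation.

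**Working it through.** **Inputs from the documents**
- Male limit: 13 mg/l (Protocol Section 4.3, no. 16, and Protocol Outline).
- Female limit: 11.3 mg/l (same places).
- Sample volumes and counts: Protocol Appendix 3.

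**Input assumed.** The documents give no range for haemoglobin. I take 20 to 170 g/l, deliberately wide at the low end. A narrower range of 60 to 170 g/l was also tried.

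The plan shows no calculation behind the limit, so there is no derivation to reproduce. The check is a unit conversion.

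**Step 1. Convert to g/l** (mg/l ÷ 1000)
- Male: 13 ÷ 1000 = 0.013 g/l.
- Female: 11.3 ÷ 1000 = 0.0113 g/l.

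**Step 2. Compare with possible results** (result ÷ limit)

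| Assumed result | Ratio to 0.013 g/l |
|---|---|
| 20 g/l | 20 ÷ 0.013 ≈ 1,538 |
| 60 g/l | 60 ÷ 0.013 ≈ 4,615 |
| 170 g/l | 170 ÷ 0.013 ≈ 13,077 |

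No result in either range comes within a factor of 1,000 of the limit, so the number excluded by criterion 16 as written is 0.

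**Step 3. Would changing only mg to g repair it?** The limit would become 13 g/l, and 20 ÷ 13 ≈ 1.5. The lowest assumed result is still above it, so the criterion would remain inert. Value and unit therefore have to be confirmed as a pair.

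**Step 4. Is it corrected elsewhere?** The two printings agree with each other, which makes a PDF-reading fault unlikely. Section 7.2.2 names haemoglobin without a unit. The SAP has no limit. Nothing in the documents shows what was intended.

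**Step 5. When can the criterion act?** By its own words it applies at screening. Protocol Section 4.3 then states "The following exclusion criteria 7, 8, 9, 10, 11, 12 and 20 will be re-checked at Day -1 visit"; number 16 is not among them, and the schedule in Section 7.1 has no haematology on Day -1. The screening check is therefore its one scheduled use.

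**Context only: blood drawn**
- Screening: 3.5 + 4 + 3.5 = 11 mL.
- Day 1 to Day 11: (4 × 2) + (22 × 4) + (25 × 5) + (25 × 10) + 3.5 + 4 = 8 + 88 + 125 + 250 + 7.5 = 478.5 mL.
- Sum: 11 + 478.5 = 489.5 mL, which agrees with the Appendix 3 line "Total vol (mL) per subject".

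The documents do not link criterion 16 to this volume, and Appendix 3 contains no error here.

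**The case against.** The strongest reply is that this is an obvious slip in a unit. Site staff would see at once that the printed unit cannot be meant, and nothing shows that anyone would apply it literally. The eCRF and laboratory manual, which might settle the matter, are not available. That is fair: the misprint is certain, its practical effect is not. But a reader who sees that the unit is wrong still has to guess the value and unit intended, and the documents offer no help.

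Other safeguards also stand. Exclusion 3 and the local laboratory's normal ranges can catch a low value, and an abnormal result that looks temporary may be repeated once before treatment, with screen failure if it persists. Exclusion 7 covers recent blood donation or loss of 450 mL or more, and inclusion 6 requires good physical status; both are re-checked on Day -1. These narrow the consequence, but none supplies a numeric haemoglobin limit.

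Two further points are right. Leaving criterion 16 off the Day -1 list is consistent with a criterion defined at screening and with the schedule, so it is not a defect in itself. The blood volume is background and adds no weight. Removing the female limit is tidying: it changes no eligibility decision.

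**Conclusion.** The concern holds. As printed, exclusion criterion 16 excludes 0 subjects: its male limit of 0.013 g/l is more than 1,000 times below every result in the assumed range. That range is the only outside assumption, and the conclusion is the same from 20 or from 60 g/l upwards. The statement that a change of unit alone would leave the limit inert rests on the same assumption.

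The consequence is limited to eligibility screening and to how deviations from this criterion would be recorded. PK estimates, analysis set definitions, schedule and sampling do not change, and exclusion by judgement remains possible. It should be corrected because it is a decision threshold that cannot work as written, but it does not threaten the trial's results.

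**What to change.** - The sponsor should confirm the intended male haemoglobin value and its unit together. No value is proposed here; the documents do not show which was meant.
- Correct criterion 16 identically in the Protocol Outline and in Section 4.3.
- Delete the female limit while the text is open.
- Check that any eCRF eligibility check uses the same value and unit.

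The cost is protocol wording in two places, through an amendment or clarification memo. Visits, samples and analyses stay as they are.

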#### **4.4 Subject Withdrawals**

Subjects must be discontinued from the study for any of the following reasons:

- An adverse event occurs that, in the opinion of the investigator, makes it unsafe for the subject to continue in the study. In this case, the appropriate measures will be taken.
- The subject is lost to follow-up.
- The subject withdraws consent.
- The subject's safety is affected by violation of inclusion or exclusion criteria or use of not-permitted concomitant medication.
- The subject is unwilling or unable to adhere to the study requirements, i.e., non-compliance.
- The sponsor or the regulatory authorities or the Ethics Committee(s), for any reason, terminates the entire study, or terminates the study for this trial site or this particular subject.

It is understood by all concerned that an excessive rate of withdrawals can render the study uninterpretable; therefore, unnecessary withdrawals of subjects should be avoided.

However, should a subject discontinue the study, all efforts will be made to complete and report the observations as thoroughly as possible.

In case of withdrawal, the Investigator must fill in the "Study Termination" page in the eCRF, reporting the main reason for withdrawal.

In case actual drop-out rate is higher than expected, additional subjects may be enrolled in order to reach a suitable number (at least 6) evaluable subjects.

If a subject is withdrawn/drops-out of the study after receiving the test treatment, the subject study number and corresponding test treatments should not be reassigned to another subject.

Clinical Study Code: CLI-06001AA1-02	Version No.: 1.0
EUDRACT No.: 2020-004201-31	Date: 19 October 2020

## 5. CONCOMITANT MEDICATIONS

### 5.1 Permitted concomitant Medications

Occasional paracetamol (maximum 2 g per day with a maximum of 10 g per 14 days for mild conditions not meeting exclusion criteria).

### 5.2 Non-permitted concomitant Medications

- Intake of any enzyme-inducing drugs, enzyme-inhibiting drugs, biologic drugs or any drug known to have a well-defined potential for hepatotoxicity (e.g. isoniazide, nimesulide, ketoconazole) are not permitted within 3 months prior to screening and throughout the study period (including the follow up period)
- Intake of any drug treatment, including prescribed or OTC medicines, vitamins, homeopathic remedies etc., with the exception of the allowed concomitant medications specified in the relative section are not permitted within 14 days prior to screening and throughout the study period including the follow up period

In case of intake of any forbidden concomitant medication during the study the need for this subject to be withdrawn from the study will be carefully evaluated by the Investigator on the basis of the potential impact on the study outcome and/or safety evaluation in the subject's best interest.

